Diarrhea Adult and Pediatric ≥ 1 Year Pediatric < 1 Year	Transient or intermittent episodes of unformed stools OR Increase of ≤ 3 stools over baseline/24 hr Liquid stools (more unformed than usual) but usual number of stools	Persistent episodes of unformed to watery stools OR Increase of 4–6 stools over baseline per 24 hrs. Liquid stools with increased number of stools OR Mild dehydration	Bloody diarrhea OR Increase of ≥ 7 stools per 24-hour period OR IV fluid replacement indicated Liquid stools with moderate dehydration	Life-threatening consequences (eg, hypotensive shock) Liquid stools resulting in severe dehydration with aggressive rehydration indicated OR Hypotensive shock
Dysphagia-Odynophagia	Symptomatic but able to eat usual diet	Symptoms causing altered dietary intake without medical intervention indicated	Symptoms causing severely altered dietary intake with medical intervention indicated	Life-threatening reduction in oral intake

GASTROINTESTINAL				
	Grade 1	Grade 2	Grade 3	Grade 4
Mucositis/Stomatitis (clinical exam) See also Proctitis, Dysphagia-Odynophagia	Erythema of the mucosa	Patchy pseudomembranes or ulcerations	Confluent pseudomembranes or ulcerations OR Mucosal bleeding with minor trauma	Tissue necrosis OR Diffuse spontaneous mucosal bleeding OR Life-threatening consequences (eg, aspiration, choking)
Nausea	Transient (< 24 hours) or intermittent nausea with no or minimal interference with oral intake	Persistent nausea resulting in decreased oral intake for 24–48 hours	Persistent nausea resulting in minimal oral intake for > 48 hours OR Aggressive rehydration indicated (eg, IV fluids)	Life-threatening consequences (eg, hypotensive shock)
Pancreatitis	NA	Symptomatic AND Hospitalization not indicated (other than ER visit)	Symptomatic AND Hospitalization indicated (other than ER visit)	Life-threatening consequences (eg, sepsis, circulatory failure, hemorrhage)
Proctitis (functional-symptomatic) Also see Mucositis/Stomatitis for Clinical Exam	Rectal discomfort AND No intervention indicated	Symptoms causing greater than minimal interference with usual social & functional activities OR Medical intervention indicated	Symptoms causing inability to perform usual social/functional activities OR Operative intervention indicated	Life-threatening consequences (eg, perforation)
Vomiting	Transient or intermittent vomiting with no or minimal interference with oral intake	Frequent episodes of vomiting with no or mild dehydration	Persistent vomiting resulting in orthostatic hypotension OR Aggressive rehydration indicated	Life-threatening consequences (eg, hypotensive shock)

NEUROLOGICAL				
	Grade 1	Grade 2	Grade 3	Grade 4
Alteration in Personality-Behavior or in Mood (eg, agitation, anxiety, depression, mania, psychosis)	Alteration causing no or minimal interference with usual social & functional activities	Alteration causing greater than minimal interference with usual social & functional activities	Alteration causing inability to perform usual social & functional activities	Behavior potentially harmful to self or others (eg, suicidal/homicidal ideation or attempt, acute psychosis) OR Causing inability to perform basic self-care functions
Altered Mental Status For Dementia, see Cognitive and Behavioral/Attentional Disturbance (including dementia and ADD)	Changes causing no or minimal interference with usual social & functional activities	Mild lethargy or somnolence causing greater than minimal interference with usual social & functional activities	Confusion, memory impairment, lethargy, or somnolence causing inability to perform usual social & functional activities	Delirium OR obtundation, OR coma
Ataxia	Asymptomatic ataxia detectable on exam OR Minimal ataxia causing no or minimal interference with usual social & functional activities	Symptomatic ataxia causing greater than minimal interference with usual social & functional activities	Symptomatic ataxia causing inability to perform usual social & functional activities	Disabling ataxia causing inability to perform basic self-care functions
Cognitive and Behavioral/Attentional Disturbance (including dementia and Attention Deficit Disorder)	Disability causing no or minimal interference with usual social & functional activities OR Specialized resources not indicated	Disability causing greater than minimal interference with usual social & functional activities OR Specialized resources on part-time basis indicated	Disability causing inability to perform usual social & functional activities OR Specialized resources on a full-time basis indicated	Disability causing inability to perform basic self-care functions OR Institutionalization indicated
CNS Ischemia (acute)	NA	NA	Transient ischemic attack	Cerebral vascular accident (CVA, stroke) with neurological deficit
Developmental delay – Pediatric ≤ 16 Years	Mild developmental delay, either motor or cognitive, as determined by comparison with a developmental screening tool appropriate for the setting	Moderate developmental delay, either motor or cognitive, as determined by comparison with a developmental screening tool appropriate for the setting	Severe developmental delay, either motor or cognitive, as determined by comparison with a developmental screening tool appropriate for the setting	Developmental regression, either motor or cognitive, as determined by comparison with a developmental screening tool appropriate for the setting

NEUROLOGICAL				
	Grade 1	Grade 2	Grade 3	Grade 4
Headache	Symptoms causing no or minimal interference with usual social & functional activities	Symptoms causing greater than minimal interference with usual social & functional activities	Symptoms causing inability to perform usual social & functional activities	Symptoms causing inability to perform basic self-care functions OR Hospitalization indicated (other than ER visit) OR Headache with significant impairment of alertness or other neurologic function
Insomnia	NA	Difficulty sleeping causing greater than minimal interference with usual social/functional activities	Difficulty sleeping causing inability to perform usual social & functional activities	Disabling insomnia causing inability to perform basic self-care functions
Neuromuscular Weakness (including myopathy & neuropathy)	Asymptomatic with decreased strength on exam OR Minimal muscle weakness causing no or minimal interference with usual social & functional activities	Muscle weakness causing greater than minimal interference with usual social & functional activities	Muscle weakness causing inability to perform usual social & functional activities	Disabling muscle weakness causing inability to perform basic self-care functions OR Respiratory muscle weakness impairing ventilation
Neurosensory Alteration (including paresthesia and painful neuropathy)	Asymptomatic with sensory alteration on exam or minimal paresthesia causing no or minimal interference with usual social & functional activities	Sensory alteration or paresthesia causing greater than minimal interference with usual social & functional activities	Sensory alteration or paresthesia causing inability to perform usual social & functional activities	Disabling sensory alteration or paresthesia causing inability to perform basic self-care functions
Seizure: (new onset)	NA	1 seizure	2–4 seizures	Seizures of any kind that are prolonged, repetitive (eg, status epilepticus), or difficult to control (eg, refractory epilepsy)

NEUROLOGICAL				
	Grade 1	Grade 2	Grade 3	Grade 4
Seizure: (pre-existing) For Worsening of Existing Epilepsy the Grades Should Be Based on an Increase from Previous Level of Control to Any of These Levels	NA	Increased frequency of pre-existing seizures (non-repetitive) without change in seizure character OR infrequent breakthrough seizures while on stable meds in a previously controlled seizure disorder	Change in seizure character from baseline either in duration or quality (eg, severity or focality)	Seizures of any kind that are prolonged, repetitive (eg, status epilepticus), or difficult to control (eg, refractory epilepsy)
Seizure – Pediatric < 18 Years	Seizure, generalized onset with or without secondary generalization, lasting < 5 minutes with < 24 hours post ictal state	Seizure, generalized onset with or without secondary generalization, lasting 5–20 minutes with < 24 hours post ictal state	Seizure, generalized onset with or without secondary generalization, lasting > 20 minutes	Seizure, generalized onset with or without secondary generalization, requiring intubation and sedation
Syncope (not associated with a procedure)	NA	Present	NA	NA
Vertigo	Vertigo causing no or minimal interference with usual social & functional activities	Vertigo causing greater than minimal interference with usual social & functional activities	Vertigo causing inability to perform usual social & functional activities	Disabling vertigo causing inability to perform basic self-care functions

MUSCULOSKELETAL				
	Grade 1	Grade 2	Grade 3	Grade 4
Arthralgia See also Arthritis	Joint pain causing no or minimal interference with usual social & functional activities	Joint pain causing greater than minimal interference with usual social & functional activities	Joint pain causing inability to perform usual social & functional activities	Disabling joint pain causing inability to perform basic self-care functions
Arthritis See also Arthralgia	Stiffness or joint swelling causing no or minimal interference with usual social & functional activities	Stiffness or joint swelling causing greater than minimal interference with usual social & functional activities	Stiffness or joint swelling causing inability to perform usual social & functional activities	Disabling joint stiffness or swelling causing inability to perform basic self-care functions
Bone Mineral Loss Pediatric < 21 Years	BMD t-score or z-score -2.5 to -1.0 BMD z-score -2.5 to -1.0	BMD t-score or z-score < -2.5 BMD z-score < -2.5	Pathological fracture (including loss of vertebral height) Pathological fracture (including loss of vertebral height)	Pathologic fracture causing life-threatening consequences Pathologic fracture causing life-threatening consequences
Myalgia (non-injection site)	Muscle pain causing no or minimal interference with usual social & functional activities	Muscle pain causing greater than minimal interference with usual social & functional activities	Muscle pain causing inability to perform usual social & functional activities	Disabling muscle pain causing inability to perform basic self-care functions
Osteonecrosis	NA	Asymptomatic with radiographic findings AND No operative intervention indicated	Symptomatic bone pain with radiographic findings OR Operative intervention indicated	Disabling bone pain with radiographic findings causing inability to perform basic self-care functions

SYSTEMIC				
	Grade 1	Grade 2	Grade 3	Grade 4
Acute Systemic Allergic Reaction	Localized urticaria (wheals) with no medical intervention indicated	Localized urticaria with medical intervention indicated OR Mild angioedema with no medical intervention indicated	Generalized urticaria OR Angioedema with medical intervention indicated OR Symptomatic mild bronchospasm	Acute anaphylaxis OR Life-threatening bronchospasm OR laryngeal edema
Chills	Symptoms causing no or minimal interference with usual social & functional activities	Symptoms causing greater than minimal interference with usual social & functional activities	Symptoms causing inability to perform usual social & functional activities	NA
Fatigue Malaise	Symptoms causing no or minimal interference with usual social & functional activities	Symptoms causing greater than minimal interference with usual social & functional activities	Symptoms causing inability to perform usual social & functional activities	Incapacitating fatigue/malaise symptoms causing inability to perform basic self-care functions
Fever (nonaxillary)	37.7°C to 38.6°C 99.8°F to 101.5°F	38.7°C to 39.3°C 101.6°F to 102.8°F	39.4°C to 40.5°C 102.9°F to 104.9°F	> 40.5°C > 104.9°F
Pain- Indicate Body Site See also Injection Site Pain, Headache, Arthralgia, and Myalgia	Pain causing no or minimal interference with usual social & functional activities	Pain causing greater than minimal interference with usual social & functional activities	Pain causing inability to perform usual social & functional activities	Disabling pain causing inability to perform basic self-care functions OR Hospitalization (other than ER visit) indicated
Unintentional Weight Loss	NA	5% to 9% loss in body weight from baseline	10% to 19% loss in body weight from baseline	≥ 20% loss in body weight from baseline OR Aggressive intervention indicated [eg, tube feeding or total parenteral nutrition]

INJECTION SITE REACTION				
	Grade 1	Grade 2	Grade 3	Grade 4
Injection Site Pain (pain without touching) Or Tenderness (pain when area is touched)	Pain/tenderness causing no or minimal limitation of use of limb	Pain/tenderness limiting use of limb OR Pain/tenderness causing greater than minimal interference with usual social & functional activities	Pain/tenderness causing inability to perform usual social & functional activities	Pain/tenderness causing inability to perform basic self-care function OR Hospitalization (other than ER visit) indicated for management of pain/tenderness
Injection Site Reaction (Localized), > 15 Years Pediatric ≤ 15 Years	Erythema OR Induration of 5 × 5 cm to 9 × 9 cm (or 25–81 × cm ²) Erythema OR Induration OR Edema present but ≤ 2.5 cm diameter	Erythema OR Induration OR Edema > 9 cm any diameter (or > 81 cm ²) Erythema OR Induration OR Edema > 2.5 cm diameter but < 50% surface area of the extremity segment (eg, upper arm/thigh)	Ulceration OR Secondary infection OR Phlebitis OR Sterile abscess OR Drainage Erythema OR Induration OR Edema involving ≥ 50% surface area of the extremity segment (eg, upper arm/thigh) OR Ulceration OR Secondary infection OR Phlebitis OR Sterile abscess OR Drainage	Necrosis (involving dermis and deeper tissue) Necrosis (involving dermis and deeper tissue)
Pruritis Associated with Injection See also Skin: Pruritis (itching—no skin lesions)	Itching localized to injection site AND Relieved spontaneously or with < 48 h treatment	Itching beyond the injection site but not generalized OR Itching localized to injection site requiring ≥ 48 h treatment	Generalized itching causing inability to perform usual social & functional activities	NA

ENDOCRINE/METABOLIC				
	Grade 1	Grade 2	Grade 3	Grade 4
Lipodystrophy (eg, back of neck, breasts, abdomen)	Detectable by study participant or caregiver (for young children and disabled adults)	Detectable on physical exam by health care provider	Disfiguring OR Obvious changes on casual visual inspection	NA
Diabetes Mellitus	NA	New onset without need to initiate medication OR Modification of current meds to regain glucose control	New onset with initiation of indicated med OR Diabetes uncontrolled despite treatment modification	Life-threatening consequences (eg, ketoacidosis, hyperosmolar non-ketotic coma)
Gynecomastia	Detectable by study participant or caregiver (for young children and disabled adults)	Detectable on physical exam by health care provider	Disfiguring OR Obvious on casual visual inspection	NA
Hyperthyroidism	Asymptomatic	Symptomatic causing greater than minimal interference with usual social & functional activities OR Thyroid suppression therapy indicated	Symptoms causing inability to perform usual social & functional activities OR Uncontrolled despite treatment modification	Life-threatening consequences (eg, thyroid storm)
Hypothyroidism	Asymptomatic	Symptomatic causing greater than minimal interference with usual social & functional activities OR Thyroid replacement therapy indicated	Symptoms causing inability to perform usual social & functional activities OR Uncontrolled despite treatment modification	Life-threatening consequences (eg, myxedema coma)
Lipoatrophy (eg, fat loss from the face, extremities, buttocks)	Detectable by study participant or caregiver (for young children and disabled adults)	Detectable on physical exam by health care provider	Disfiguring OR Obvious on casual visual inspection	NA

GENITOURINARY				
	Grade 1	Grade 2	Grade 3	Grade 4
Intermenstrual Bleeding (IMB)	Spotting observed by participant OR Minimal blood observed during clinical or colposcopic exam	Intermenstrual bleeding not greater in duration or amount than usual menstrual cycle	Intermenstrual bleeding greater in duration or amount than usual menstrual cycle	Hemorrhage with life-threatening hypotension OR Operative intervention indicated
Urinary Tract obstruction (eg, stone)	NA	Signs or symptoms of urinary tract obstruction without hydronephrosis or renal dysfunction	Signs or symptoms of urinary tract obstruction with hydronephrosis or renal dysfunction	Obstruction causing life-threatening consequences

INFECTION				
	Grade 1	Grade 2	Grade 3	Grade 4
Infection (any other than HIV infection)	Localized, no systemic antiꞵbial treatment indicated AND Symptoms causing no or minimal interference with usual social & functional activities	Systemic antiꞵbial treatment indicated OR Symptoms causing greater than minimal interference with usual social & functional activities	Systemic antiꞵbial treatment indicated AND Symptoms causing inability to perform usual social & functional activities OR Operative intervention (other than simple incision and drainage) indicated	Life-threatening consequences (eg, septic shock)

Basic Self-care Functions: Activities such as bathing, dressing, toileting, transfer/movement, continence, and feeding.

Usual Social & Functional Activities: Adaptive tasks and desirable activities, such as going to work, shopping, cooking, use of transportation, pursuing a hobby, etc.

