3.1.2. Treatment Phase

The Treatment Phase will be initiated sequentially by age group as defined in Cohort 1, 2, and 3 of the PK Lead-in. Subjects who participated in PK Lead-in phase will immediately rollover into Treatment Phase with no interruption of study drug administration until the appropriateness of the dose has been confirmed by PK and safety results from the PK Lead-in. The first visit in the Treatment Phase for these subjects will be the Week 2 visit. Additional subjects will be enrolled in the Treatment Phase of each Cohort upon confirmation of the appropriateness of the dose from the PK Lead-in.

Children aged 3 to < 12 years (Group 2) and adolescents aged 12 to < 18 years (Group 1) with chronic HCV-infection and a HCV RNA \geq 1000 IU/mL at study entry (those who were dosed in the PK Lead-in phase will have met this criteria prior to enrollment) will be evaluated.

Subjects enrolled in the Treatment Phase will receive the following regimen:

a) United Kingdom:

- GT-1, GT-4, GT-5, & GT-6 treatment-naïve subjects with or without cirrhosis: LDV/SOF FDC for 12 weeks
- GT-1, GT-4, GT-5, & GT-6 treatment-experienced subjects without cirrhosis: LDV/SOF FDC for 12 weeks
- GT-1, GT-4, GT-5, & GT-6 treatment-experienced subjects with cirrhosis: LDV/SOF FDC for 24 weeks
- GT-3 treatment-experienced subjects with or without cirrhosis: LDV/SOF FDC + RBV for 24 weeks

b) United States/Australia/New Zealand:

- GT-1 treatment-naïve subjects with or without cirrhosis: LDV/SOF FDC for 12 weeks
- GT-1 treatment-experienced subjects without cirrhosis: LDV/SOF FDC for 12 weeks
- GT-1 treatment-experienced subjects with cirrhosis: LDV/SOF FDC for 24 weeks
- GT-4, GT-5, & GT-6 treatment-naïve or treatment-experienced subjects with or without cirrhosis: LDV/SOF FDC for 12 weeks

Table 3-1. Subject Enrollment by HCV Genotype, Country, and Treatment Duration

	GT-1			GT-3	GT-4, GT-5, & GT-6		
	Cirrhotic or Non-cirrhotic Subjects (TN)	Non-cirrhotic Subjects (TE)	Cirrhotic Subjects (TE)	Non-cirrhotic or Cirrhotic Subjects (TE)	Cirrhotic or Non-cirrhotic Subjects (TN)	Non-cirrhotic Subjects (TE)	Cirrhotic Subjects (TE)
United States	12 Weeks of treatment with LDV/SOF FDC	12 Weeks of treatment with LDV/SOF FDC	24 Weeks of treatment with LDV/SOF FDC	N/A	12 Weeks of treatment with LDV/SOF FDC	12 Weeks of treatment with LDV/SOF FDC	12 Weeks of treatment with LDV/SOF FDC

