Australia	12 Weeks of treatment with LDV/SOF FDC	12 Weeks of treatment with LDV/SOF FDC	24 Weeks of treatment with LDV/SOF FDC	N/A	12 Weeks of treatment with LDV/SOF FDC	12 Weeks of treatment with LDV/SOF FDC	12 Weeks of treatment with LDV/SOF FDC
New Zealand	12 Weeks of treatment with LDV/SOF FDC	12 Weeks of treatment with LDV/SOF FDC	24 Weeks of treatment with LDV/SOF FDC	N/A	12 Weeks of treatment with LDV/SOF FDC	12 Weeks of treatment with LDV/SOF FDC	12 Weeks of treatment with LDV/SOF FDC
United Kingdom	12 Weeks of treatment with LDV/SOF FDC	12 Weeks of treatment with LDV/SOF FDC	24 Weeks of treatment with LDV/SOF FDC	24 Weeks of treatment with LDV/SOF FDC + RBV	12 Weeks of treatment with LDV/SOF FDC	12 Weeks of treatment with LDV/SOF FDC	24 Weeks of treatment with LDV/SOF FDC

TN = Treatment Naïve, TE = Treatment Experienced, N/A = Not Applicable

Subjects with GT -1, -3, and -4 were enrolled initially. GT-5 and GT-6 subjects will be included in those groups/cohorts actively enrolling subjects given confirmation of benefit:risk in adult patients has been obtained. If emerging LDV/SOF FDC data in GT-2 support treatment in adults, pediatric subjects with GT-2 will be subsequently enrolled.

The study will enroll both treatment naïve and treatment experienced pediatric subjects with up to 40 subjects allowed to be treatment experienced. Approximately 220 subjects, including subjects from the PK Lead-in Phase, will be enrolled in the Treatment Phase as follows:

- Group 1: Approximately 100 adolescent subjects (12 to < 18 years of age)
- Group 2: Approximately 120 pediatric subjects (3 to < 12 years of age)

The following definitions will be used for treatment experienced subjects:

- Interferon intolerant: Subject who discontinued therapy (≤ 12 weeks total) due to ≥ 1 adverse event
- Interferon non-responder: Subject who did not achieve undetectable HCV RNA levels while on treatment
- Relapse/breakthrough: Subject who achieved undetectable HCV RNA during treatment or within 4 weeks of the end of treatment but did not achieve a sustained virologic response (SVR)

All subjects who do not attain SVR or have viral relapse will be encouraged to discuss treatment with SOC therapy with their healthcare provider.

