7.2. Subject Stopping Rules for LDV/SOF FDC and RBV

The Gilead Medical Monitor should be consulted prior to dose discontinuation of LDV/SOF FDC unless the investigator believes that immediate action is warranted to ensure the continued safety of the subject.

Administration of LDV/SOF FDC may be discontinued due to a clinical or laboratory event. There is no option for LDV/SOF FDC dose reduction. If LDV/SOF FDC is stopped for toxicity, it should not be restarted, RBV should be stopped (GT-3 subjects only), and the subject should complete an Early Termination Visit.

Subjects who meet any of the following laboratory criteria must stop treatment with LDV/SOF FDC:

- Elevation of ALT and/or AST >5× Day 1 or nadir, confirmed by immediate repeat testing
- Abnormal elevation of ALT >3× Day 1 and total bilirubin >2 × ULN, confirmed by immediate repeat testing
- Confirmed elevation of ALT >15 × ULN, confirmed by immediate repeat testing
- Any Grade 3 or greater rash associated with constitutional symptoms
- Any Grade 4 event or lab abnormality assessed as related to treatment with LDV/SOF FDC

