8.2.2. Assessment of Severity

The severity grading of AEs will be assessed as Grade 1, 2, 3, or 4 using the GSI Grading Scale for Severity of Adverse Events and Laboratory Abnormalities ([Appendix 3](#)).

For AEs associated with laboratory abnormalities, the event should be graded on the basis of the clinical severity in the context of the underlying conditions; this may or may not be in agreement with the grading of the laboratory abnormality.

8.3. Investigator Requirements and Instructions for Reporting Adverse Events and Serious Adverse Events to Gilead or CRO

Requirements for collection prior to study drug initiation:

After informed consent, but prior to initiation of study medication, the following types of events should be reported on the case report form (CRF/eCRF): all SAEs and adverse events related to protocol-mandated procedures.

Adverse Events

Following initiation of study medication, collect all AEs, regardless of cause or relationship, until 4 weeks after last administration of study drug must be reported to the CRF/eCRF database as instructed.

All AEs should be followed up until resolution or until the adverse event is stable, if possible. Gilead Sciences may request that certain AEs be followed beyond the protocol defined follow up period.

Serious Adverse Events

All SAEs, regardless of causal relationship, that occurs after the subject first consents to participate in the study (i.e., signing the informed consent) and throughout the duration of the study, including the protocol-required 24-week post treatment follow-up period, must be reported to the CRF/eCRF database and Gilead Drug Safety and Public Health (DSPH) as instructed. This also includes any SAEs resulting from protocol-mandated procedures performed after informed consent is signed.

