Alkaline Phosphatase	1.25 to 2.50 × ULN	> 2.50 to 5.00 × ULN	> 5.00 to 10.00 × ULN	> 10.00 × ULN
Total Amylase	> 1.0 to 1.5 × ULN	> 1.5 to 2.0 × ULN	> 2.0 to 5.0 × ULN	> 5.0 × ULN
Pancreatic Amylase	> 1.0 to 1.5 × ULN	> 1.5 to 2.0 × ULN	> 2.0 to 5.0 × ULN	> 5.0 × ULN
Lipase	> 1.0 to 1.5 × ULN	> 1.5 to 3.0 × ULN	> 3.0 to 5.0 × ULN	> 5.0 × ULN
Albumin Pediatrics <16 years	-	2.0 to < LLN g/dL 20 to < LLN g/L	< 2.0 g/dL < 20 g/L	NA
≥ 16 years	3.0 g/dL to < LLN 30 g/L to < LLN	2.0 to < 3.0 g/dL 20 to < 30 g/L	< 2.0 g/dL < 20 g/L	NA

URINALYSIS				
	Grade 1	Grade 2	Grade 3	Grade 4
Hematuria (Dipstick)	1+	2+	3-4+	NA
Hematuria (Quantitative) See Note below				
Females	>ULN - 10 RBC/HPF	> 10-75 RBC/HPF	> 75 RBC/HPF	NA
Males	6-10 RBC/HPF	> 10-75 RBC/HPF	> 75 RBC/HPF	NA
Proteinuria (Dipstick)	1+	2-3+	4+	NA
Proteinuria, 24 Hour Collection				
Adult and Pediatric ≥ 10 Years	200 to 999 mg/24 h	>999 to 1999 mg/24 h	>1999 to 3500 mg/24 h	> 3500 mg/24 h
Pediatric > 3 Mo to < 10 Years	201 to 499 mg/m ² /24 h	>499 to 799 mg/m ² /24 h	>799 to 1000 mg/m ² /24 h	> 1000 mg/ m ² /24 h
Glycosuria (Dipstick)	1+	2-3+	4+	NA

Notes:

- Toxicity grades for Quantitative and Dipstick Hematuria will be assigned by Covance Laboratory, however for other laboratories, toxicity grades will only be assigned to Dipstick Hematuria.
- With the exception of lipid tests, any graded laboratory test with a result that is between the LLN and ULN should be assigned Grade 0.
- If the severity of a clinical AE could fall under either one of two grades (e.g., the severity of an AE could be either Grade 2 or Grade 3), select the higher of the two grades for the AE.

CARDIOVASCULAR				
	Grade 1	Grade 2	Grade 3	Grade 4
Cardiac Arrhythmia (general) (By ECG or physical exam)	Asymptomatic AND No intervention indicated	Asymptomatic AND Non-urgent medical intervention indicated	Symptomatic, non-life-threatening AND Non-urgent medical intervention indicated	Life-threatening arrhythmia OR Urgent intervention indicated
Cardiac-ischemia/Infarction	NA	NA	Symptomatic ischemia (stable angina) OR Testing consistent with ischemia	Unstable angina OR Acute myocardial infarction
Hemorrhage (significant acute blood loss)	NA	Symptomatic AND No transfusion indicated	Symptomatic AND Transfusion of ≤ 2 units packed RBCs (for children ≤ 10 cc/kg) indicated	Life-threatening hypotension OR Transfusion of > 2 units packed RBCs indicated (for children ≤ 10 cc/kg) indicated

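### Appendix 3 prints the same child transfusion limit (≤ 10 cc/kg) for Grade 3 and Grade 4 haemorrhage, so small transfusions become Grade 4 and larger ones fit no transfusion criterion

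*Protocol*

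**What the plan says.** Protocol Section 8.2.2 fixes the scale: "The severity grading of AEs will be assessed as Grade 1, 2, 3, or 4 using the GSI Grading Scale". That scale is Appendix 3.

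In its Cardiovascular table, the Hemorrhage row has these criteria:

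- **Grade 2:** symptomatic, with no transfusion indicated.
- **Grade 3:** symptomatic, and "Transfusion of ≤ 2 units packed RBCs (for children ≤ 10 cc/kg) indicated".
- **Grade 4:** life-threatening hypotension, or "Transfusion of > 2 units packed RBCs indicated (for children ≤ 10 cc/kg) indicated".

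For a clinical event that could fall under either of two grades, the notes in the same appendix tell the grader to "select the higher of the two grades for the AE".

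Section 7.2 lists criteria for a mandatory stop of LDV/SOF. One is "Any Grade 4 event or lab abnormality assessed as related to treatment with LDV/SOF FDC". The same section adds: "If LDV/SOF FDC is stopped for toxicity, it should not be restarted". Section 9.1.2 makes any adverse event leading to permanent discontinuation of study drug the primary safety endpoint of the Treatment Phase.

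Neither document gives another child limit for Grade 4 haemorrhage.

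**The concern.** A threshold separates two grades only if its direction reverses between them. The adult limit does this and the child limit does not. The word for indicated also appears twice in the Grade 4 cell, which suggests that the Grade 3 parenthesis was carried across without changing the sign.

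Every subject is under 18 at Day 1, so the child limit is not a marginal clause here. As printed, the smaller transfusion takes the higher grade and the larger one has no fitting criterion.

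Three things are at stake:

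- **Treatment.** A related small bleed that is Grade 4 only because of this cell must end LDV/SOF permanently, and RBV with it in GT-3 subjects. As Grade 3 it would not meet that criterion, and stopping would be a judgement.
- **Primary safety endpoint.** The forced stop would count as an event.
- **AE tables.** If the grade of a large transfusion were left unrecorded because nothing fits, SAP Section 7.1.2 would tabulate it as missing, outside the Grade 3 or above counts.

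**Working it through.** The plan gives no figure to reproduce here. The check applies the printed criteria to a child's transfusion.

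**Inputs**

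- Grade 2, 3 and 4 haemorrhage criteria and the tie-break note: Protocol Appendix 3.
- Weights of 17 kg and 45 kg: the Cohort 2 weight limits in Protocol Section 3.1.1.
- Group sizes: about 120 subjects aged 3 to < 12 years and about 220 in all (Protocol Section 3.1.2).
- Volumes of 100 cc and 250 cc: my illustrations, not from the documents.

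**Step 1. Apply the criteria.** Let V = volume transfused (cc) ÷ body weight (kg), for a symptomatic child without life-threatening hypotension.

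| V | Grade 2 | Grade 3 | Grade 4 | Grade as printed |
|---|---|---|---|---|
| 0 < V ≤ 10 cc/kg | no (transfused) | met | met | 4, by the tie-break |
| V > 10 cc/kg | no (transfused) | not met | not met | none fits |

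With life-threatening hypotension the event is Grade 4 at any volume, so the flaw does not touch that case.

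**Step 2. Convert the limit to volumes.** Limit = 10 cc/kg × weight.

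- 17 kg: 10 × 17 = 170 cc
- 45 kg: 10 × 45 = 450 cc

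**Step 3. Two examples at 17 kg.**

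- 100 ÷ 17 = 5.9 cc/kg. Both cells are met, so the event is Grade 4.
- 250 ÷ 17 = 14.7 cc/kg. Neither cell is met, so no grade fits.

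**Step 4. Weight of one event in an incidence.**

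- If children means ages 3 to < 12: 1 ÷ 120 = 0.83%
- If adolescents are included: 1 ÷ 220 = 0.45%

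Both denominators are needed because the row sets no age. Section 3.1.2 uses the word for ages 3 to < 12, but other rows of Appendix 3 set their own limits: 17 years or younger for hypertension, 16 or younger for PR and QTc, and under 14 for dyspnoea.

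**Step 5. Apply the corrected cell.** With > 10 cc/kg in Grade 4, V ≤ 10 with symptoms is Grade 3 only and V > 10 is Grade 4 only. The overlap and the gap both disappear.

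**The case against.** The strongest case against has four parts.

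**The finding rests on one symbol in a machine-read table.** The cell's wording is awkward, and odd strings occur elsewhere in the appendices. However, the greater-than sign before 2 units and the less-than-or-equal sign before 10 cc/kg both survive in that one cell, so a general loss of symbols is unlikely. The sponsor should still check the source document before amending.

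**Investigators would infer the rule.** Section 8.2.2 requires a grade from 1 to 4, and the adult split shows what was meant. A bleed transfused above 10 cc/kg would probably be called Grade 4. This stands in part: the missing-grade consequence is conditional, and nothing shows that it would occur. It does not help with small transfusions, where the printed text gives a definite answer, Grade 4.

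**The stop needs many conditions together.** The bleed must be symptomatic, transfused at 10 cc/kg or less, without life-threatening hypotension, and judged related to LDV/SOF. Section 7.2 asks for Medical Monitor consultation, and Section 3.4 could lead to a stop on judgement anyway. Rarity is conceded: eligibility excludes platelets < 50,000/mm³, INR > 1.2 × ULN and prior variceal haemorrhage. Consultation, though, does not lift a mandatory stop. The Section 7.2 list is introduced as laboratory criteria, but this item names events and the list also includes rash, so clinical events are covered.

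**Little changes in the analysis.** This stands. SAP Section 7.1.6 pools Grade 3 and above, so a move from Grade 3 to Grade 4 leaves those tables as they are. Neither SVR12 nor the PK comparison uses AE grades. Misgrading small transfusions upward is also the cautious direction for safety reporting.

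**Conclusion.** The concern holds on the printed text. The child limit does not separate Grade 3 from Grade 4: it overlaps at or below 10 cc/kg and leaves a gap above it when there is no life-threatening hypotension. The consequence that matters is a mandatory, permanent stop for a related bleed that reached Grade 4 only through this cell, and its count in the primary safety endpoint.

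The size is small. One event moves an incidence by 0.83% or 0.45%, depending on which ages count as children. The documents give no basis for an expected number of events beyond the eligibility criteria, which point to few. It is a low-priority correction. The conclusion assumes that the cell reads in the source as it does here, and that sites follow the tie-break note literally.

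**What to change.** Change the child limit in the Grade 4 Hemorrhage cell to > 10 cc/kg, mirroring the adult split, once the source has been checked and the threshold clinically confirmed. In the same edit, state the age range that children covers in this row, so that it is clear whether an adolescent is graded by units or by cc/kg.

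The cost is one table cell and a clarification to sites, issued with the next amendment. It carries the usual IRB/IEC submission, and Protocol Section 10.2.1 requires approval before the change takes effect. Appendix 3 is a versioned sponsor scale dated 01 April 2015, so the departure from that version should be recorded.

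The SAP describes its treatment groups as reflecting subjects actually enrolled, so an amendment may come too late for some events. In that case, review any haemorrhage events with transfusion before database finalization, and note in the study report any grade or stop that turned on this cell.
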